## **3 Investigational Plan**

### **3.2 General Design**

This is a randomized, multicenter, comparative effectiveness trial of SCD and MSD to induce remission in patients with Crohn's Disease. Participants will be screened for eligibility criteria and if eligible, enrolled into the trial. Participants will continue on the diet to which they are randomized for 6 weeks with all food being provided to the participant during this time period. Participants will complete brief daily online surveys throughout their entire study participation, from consent to week 12. These will be used to calculate scores for the Short Crohn's Disease Activity Index (sCDAI). The primary outcome will be assessed at week 6 at an in-person visit. From weeks 7 to 12 participants will be asked to adhere to their randomized study diet on their own. At week 12 participants will be evaluated at an in-person visit.

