#### **6.2.5 End of Study Visit**

The end of study visit will take place at week 12 or at the visit where the participant withdraws or is withdrawn from the study. This visit will include a physical exam to obtain CDAI score. An sCDAI score will also be calculated. Participants will be asked to collect a stool sample at home and ship it to Penn. Stool will be shipped from Penn to LabCorp to obtain an FCP result. Participants will be asked to complete a DHQ, SIBDQ, a 24-hour dietary recall, and provide information about adverse events, medications, joint symptoms and provide health status information (physical, mental and social) to obtain a PROMIS score. Participants will also be weighed and have their blood drawn to measure hsCRP and hematocrit.

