## **6.5 Subject Withdrawal**

Participants may withdraw from the study at any time.

Participants may be withdrawn at the discretion of the investigator prior to randomization for the following reasons:

- Failure to provide the baseline stool sample
- Failure to complete at least 5 of the 7 baseline sCDAI surveys

Participants will be withdrawn from the study if they experience worsening symptoms requiring a change in their Crohn's disease treatment, the initiation of an antibiotic for gastrointestinal symptoms, and/or an increase of greater than 10mg/day of prednisone or equivalent for a non-gastrointestinal condition\*.

*\*Please see section 6.2.2 for equivalency chart*

Participants who have been randomized to one of the two diets and withdraw early from the study should complete an end of study visit and provide a stool sample at the time of withdrawal as described in section 6.2.5.

If the participant wishes to discontinue the study diet early for reasons not related to worsening Crohn's Disease (e.g., they don't like the diet), they will be asked to remain in follow-up and complete the next in-person visit at the target date of that visit (either week 6 or week 12). This will be the end of study visit.

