**Analysis of secondary outcomes (Secondary Aim 2):**

The secondary outcomes of clinical remission as assessed by the CDAI, PRO2, PRO3 reduction of hsCRP by >50% and to <5 mg/L, reduction of FCP by >50% and to a value of <250mcg/g and combined clinical remission and resolution of inflammation will be analyzed using the same methods described for the primary outcomes.

The secondary outcomes of fatigue, sleep quality, social aspects and pain interference will be measured using PROMIS short forms using the same methods as previously employed within CCFA Partners. PROMIS items are calibrated using a T score such that 50 is the mean for the general US population with a standard deviation of 10. Higher scores reflect greater level of the domain. We will compare PROMIS scores at baseline and at the end of the trial using a t-test. If there are meaningful differences in baseline scores between the treatment arms, comparison of the PROMIS measures at the end of follow-up will be adjusted for the baseline value using linear regression.

**Analysis of data from weeks 7 – 12 (Secondary Aim 3):** After week 6, participants will need to provide for the meals on their own if they choose to remain on the diet. This provides an opportunity to further assess the combined feasibility of the diets in the real world and patients' satisfaction with following the diet. Utilizing results from 24-hour dietary recalls, we will determine the proportion of patients assigned to each arm who elect to remain on the diet through week 12. We will also determine the proportion of patients who were able to discontinue steroid use by week 12 among the subgroup who were taking steroids in weeks 1-6. Finally, we will assess reasons for discontinuation of the diet among those who did not continue. Comparisons will be made using the CMH test following the principle of intention to treat. The analysis will be repeated among the subgroup of participants who achieved remission by week 6. These results will be qualitatively compared to the free text data on satisfaction and personal experience with the diets.

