#### **8.5 Subject Population(s) for Analysis**

As a comparative effectiveness study, the primary efficacy and safety analysis will use the principle of intention to treat such that all randomized patients will be included in the group that they were randomized to, regardless of the level of adherence with the assigned diet.

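### Participants who stop the diet before week 6 for non-disease reasons leave the study at week 6, so their week-12 outcomes and later adverse events go uncollected by rule

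*Combined protocol and SAP*

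**What the plan says.** Protocol 6.5 deals separately with participants who want to stop the diet for reasons such as not liking it. It says "they will be asked to remain in follow-up and complete the next in-person visit at the target date of that visit", specifies that this means "either week 6 or week 12", and adds "This will be the end of study visit". Section 6.2.5 is consistent with an early close: "The end of study visit will take place at week 12 or at the visit where the participant withdraws or is withdrawn from the study".

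Three other statements bear on this:

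- **Primary endpoint.** Protocol 3.2: "The primary outcome will be assessed at week 6 at an in-person visit".
- **Analysis population.** Protocol 8.5, speaking of the primary efficacy analysis and the safety analysis: "all randomized patients will be included in the group that they were randomized to, regardless of the level of adherence".
- **Weeks 7-12.** Protocol 8.4.2, on diet continuation and steroid discontinuation by week 12: "Comparisons will be made using the CMH test following the principle of intention to treat". SAP 5.5.2 names Fisher's exact test for the same comparisons, also under intention to treat.

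Both documents reject complete-case analysis as a breach of intention to treat.

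**The concern.** Intention to treat needs more than keeping every randomized participant in the denominator. It also needs outcomes to be sought whether or not the participant follows the assigned diet. For week 12, section 6.5 makes collection depend on a post-randomization choice: a participant who abandons the diet in weeks 1-6 is not asked for week-12 data at all.

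At stake are the secondary week-12 results and the safety comparison. Values that could have been observed must be filled in by assumption, and adverse events after week 6 are not sought. If early stopping differs between the diets, both problems differ by arm.

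**Working it through.** **1. Who is affected.** Reading 6.5 with its parenthesis on the two visits:

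| Diet stopped, non-disease reason | Next visit = end of study | Week-6 data | Week-12 data |
|---|---|---|---|
| Weeks 1-6, before the visit | Week 6 | Sought | Not sought |
| Weeks 7-12 | Week 12 | Sought | Sought |

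Imperfect adherence without a decision to stop does not trigger the rule.

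**2. The plan's own figure.** SAP 5.2 gives 97 per arm for 40% v 60%, 80% power, two-sided 5%. With pooled variance under the null:

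n = [1.960 × √(2 × 0.5 × 0.5) + 0.842 × √(0.4 × 0.6 + 0.6 × 0.4)]² / 0.20² = (1.386 + 0.583)² / 0.04 ≈ 96.9, so 97.

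This reproduces. It rests on the week-6 outcome, for which early stoppers are still seen, so the present point does not change it.

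**3. Which week-12 analyses lose data.**

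- *Between arms:* change in PROMIS to week 12, with the joint measures handled similarly (SAP 5.5.3), and steroid discontinuation by week 12 (Protocol 8.4.2, SAP 5.5.2). The footnote to Protocol 4.2 allows tapering only after week 6, so a steroid user whose participation ends at week 6 leaves before this outcome can be observed.
- *Within arm:* week-12 sCDAI, PRO2, PRO3 and FCP against baseline (SAP 5.5.2). CDAI and hsCRP are also scheduled at week 12.
- *Safety:* SAP 5.5.4 compares the proportions with adverse events by Fisher's exact test, with no allowance for follow-up time.

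Secondary objective 4 (who continues the diet) is largely spared: an early stopper can be classed as not continuing without a week-12 visit.

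**4. What fills the gap.** Continuous secondary outcomes use baseline carried forward, with last observation carried forward or multiple imputation as sensitivity analyses. Within-arm change uses a worst-case rule. For binary outcomes, the explicit failure rule (Protocol 8.4.2, SAP 5.5.2) covers loss before week 6. The broader remark on counting dropouts as failures does not say whether it reaches someone who completed week 6 and was then ended by rule. Last observation carried forward would use the observed week-6 value. Multiple imputation would have no observed week-12 value from any early stopper to learn from. Adverse events are not imputed.

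**5. How many.** The documents give no stopping rate, so the share *s* stopping before week 6 for non-disease reasons is assumed. Participants without week-12 data = 194 × *s*:

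| s (assumed) | 194 × s | About |
|---|---|---|
| 5% | 9.7 | 10 |
| 10% | 19.4 | 19 |
| 20% | 38.8 | 39 |

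**6. Adverse-event follow-up.** Taking 6 weeks for early stoppers and 12 for everyone else, mean follow-up in an arm is 12 − 6*s* weeks: 11.7 at 5% and 10.8 at 20%. If the arms sat at those two values, the ratio would be 10.8 / 11.7 = 0.92, or about 8% less observation in one arm.

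**7. What unequal loss could do (illustration only).** Suppose a week-12 yes/no outcome were compared between arms with 97 each, the true rate were 40% in everyone, and early stoppers were counted as failures. The apparent rate is 0.40 × (1 − *s*).

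| s, MSD / SCD (assumed) | Apparent rates | SCD − MSD | Two-sided rejection |
|---|---|---|---|
| 5% / 5% | 38% / 38% | 0 points | 5.0% |
| 5% / 10% | 38% / 36% | −2 points | 6.0% |
| 5% / 20% | 38% / 32% | −6 points | 14.1% |

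The plan does not clearly specify such a test in all randomized participants at week 12, so this shows the mechanism and does not predict a planned result.

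**The case against.** The strongest defence is that 6.5 protects what matters most. It keeps early stoppers until exactly the visit at which the primary endpoint is measured, with the full end-of-study assessment. Section 2 calls the secondary aims exploratory. Most week-12 disease-activity analyses are within arm. Section 8.5 refers to primary efficacy, which means week 6, and to safety. All of this stands and limits the point.

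Some mitigation also stands. Protocol 9.5 still requires known serious events after the study period to be recorded if judged possibly or definitely related. SAP 5.5.4, however, compares any adverse event and any serious event, so this covers only part of the gap.

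A reader might infer more than the documents support:

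- *That week-12 data are lost from non-adherers generally.* They are not; only stopping before week 6 has this effect.
- *That the loss must fall mainly on the SCD.* Protocol 1.4 calls the MSD much easier to follow, so a difference is plausible. But the rule costs data only while prepared food is supplied free, when the practical gap between the diets should be smaller. No rate is given for either arm.
- *That every missing week-12 value becomes baseline or failure.* The planned handling is wider than that (step 4), and adverse events are not imputed.
- *That these participants are all willing to continue.* Section 6.5 says only that they will be asked to stay until the next visit.

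What the defence does not answer is that intention to treat is stated explicitly for the weeks 7-12 comparisons and for safety, while the follow-up rule stops seeking the data that those analyses need.

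**Conclusion.** The point holds in a limited form. Section 6.5 ends follow-up at week 6 for participants who stop the diet before then for non-disease reasons, and no other section restores it. This conflicts with intention to treat as stated for weeks 7-12 and for safety. The planned between-arm results most exposed are PROMIS and joint measures at week 12, steroid discontinuation, and the adverse-event comparison. The primary endpoint, its sample size and its power are untouched.

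Its size depends on a stopping rate that the documents do not give. Over an assumed range of 5% to 20%, about 10 to 39 of 194 participants would have no week-12 data. Any imbalance between arms is possible but not established. The change is worth making because the data cannot be recovered once participants have left.

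**What to change.** In Protocol 6.5, separate stopping the diet from leaving the study. Ask participants who stop early for non-disease reasons, and who have not withdrawn consent, to complete the scheduled week-12 assessment as well as week 6. Where a visit is declined, seek at minimum the daily online surveys, PROMIS, and an adverse-event and medication contact to week 12. Align 6.2.5 with this.

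In SAP 5.5.2, state that observed values are analysed in the assigned arm, and say how a week-12 binary outcome is classified when week 6 was completed and week 12 is missing. In SAP 5.5.4, report follow-up time by arm beside the adverse-event proportions.

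The cost is a wording change and, for a minority of participants, one visit already in the schedule or continued use of existing online surveys. Some will decline, so the loss will shrink rather than vanish, but it will no longer be created by the protocol.

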## **7 Study Evaluations and Measurements**

### **7.1 Medical History**

The following information may be obtained from a combination of the participant's medical charts and/or self-report:

- Medical and surgical history
- Crohn's disease history
- Medication use
- Hospitalizations
- Laboratory test results – albumin and C. difficile colitis

### **7.2 Demographic information**

Gender, date of birth and race will be collected from each participant. Medication use will be collected at each visit.

### **7.3 Current Symptoms**

Participants' current symptoms, both Crohn's disease-related and otherwise, will be collected at each visit. Crohn's symptoms will also be collected through daily online surveys. Patient reported outcomes using PROMIS and other measures will be assessed at each visit.

### **7.4 Concomitant Medication**

Medication use will be collected at each visit. Participants will be permitted to taper their steroid dose after week 6 following the recommended tapering schedule in section 6.2.4.

### **7.5 Vital Signs**

Participants will be weighed on a scale in the clinic at each visit. Participant's height will be measured at Visit 1 using a stadiometer. Participants' seated temperature, heart rate, and blood pressure will be measured at Visit 1.

## **7.6 Laboratory Evaluations**

Fecal Calprotectin - This biomarker is a strong predictor of an outcome of importance to patients, the duration that they will remain free of symptoms of CD. It has been repeatedly demonstrated that patients with IBD who have an elevated FCP concentration have earlier relapse of disease. Thus, we will use this biomarker as a surrogate for future disease course. FCP assays will be completed by LabCorp at baseline, 6 weeks, and 12 weeks.

The DCC will provide the Site Investigators with their participants' FCP results from LabCorp after all of the participants have completed the last study visit upon request.

High Sensitivity C-Reactive Protein (hsCRP) – this is a biomarker in the blood that is a measure of inflammation in the body. Participants will have their blood drawn at baseline, week 6, and week 12. The Site Coordinator will spin the blood according to lab instructions, place the blood sample in the LabCorp lockbox at their site and inform LabCorp via phone of the blood sample. LabCorp will then pick up the sample for transport to their laboratory. Coordinators will be provided with detailed instructions for this.

Hematocrit will be measured by LabCorp at each visit as part of calculating a Crohn's Disease Activity Index (CDAI) score.

## **7.7 Plasma Collection**

Two tubes (4 tsp) of blood will be drawn and centrifuged at baseline and week 6 for plasma separation and collection. The plasma samples will be stored for future research use related to this study and other relevant health related questions. Possible use of the plasma samples include testing for serological markers or metabolites. Further blood sample processing, storage, and shipping information for the local sites can be found in the DINE-CD Study Manual of Procedures.

## **7.8 Pregnancy Testing**

Female participants will take a urine pregnancy test at screening if they have not yet reached menopause or if they have not had a hysterectomy.

## **7.9 Stool Sample Collection**

Stool samples will be collected on the days described above in sections 3.2.1 and 3.2.3. We will ask participants to categorize their samples on the Bristol Stool Chart scale. Stool collection kits, including pre-paid shipping labels, will be prepared by the DCC in advance and shipped to the participant (or given in person for participants at the University of Pennsylvania). Participants should collect a baseline sample within 28 days prior to the start of study diet and no more than 28 days from the initial form of consent. Participants should collect a sample for visit 6 during days 38-40 and for week 12 during days 80-82. They will ship the samples to [name] lab at the University of Pennsylvania. Shipping will be pre-paid by the Data Coordinating Center.

## **7.10 Sample preparation, processing, and storage**

Stool sample collection kits will be prepared at the DCC and sent directly to the participants' homes from the DCC. Participants will collect their samples at home, put a sample amount of stool into one 10 ml Sarstedt spoon-top vial with 5mL of 100% ethanol, and ship back the ethanol aliquot and remaining sample to the DCC. At all visits the lab will also aliquot some sample into a container provided from LabCorp labeled with participant ID and Date of Birth and send to LabCorp for FCP testing. Remaining de-identified sample labeled with the unique study ID number will be aliquoted into 4 empty 10mL Sarstedt spoon-top vials and one stock tube. The four frozen aliquots, one ethanol aliquot and one stock tube will be stored in a -80°C freezer. Once the lab has enough to create a batch shipment, they will ship aliquots in batch to Biostorage Technologies, a biobank who contracts with CCF to store CCF study samples. Samples from this study will be stored there for later use.

Four tubes of blood will be collected at baseline, three tubes will be drawn at week 6, and two tubes will be drawn week 12. All will be centrifuged according to instructions from the DCC. Two tubes will be packaged and placed in the site's LabCorp lock box for pick-up by LabCorp staff (applicable at all visits). These sample will be tested by LabCorp for hsCRP and HCT. The third and fourth tubes at baseline and

week 6 will be for plasma separation. Plasma will be aliquoted and frozen within one hour of collection in a -80°C freezer at the site. Plasma samples will be stored locally in a -80 freezer and shipped in batch to Biostorage at the end of the study. Processing, storage, and shipping instructions can be found in the DINE-CD Manual of Operating Procedures.

### **7.11 Other Evaluations, Measures**

24-hour dietary recalls will be used to assure adherence with the study diet. A trained dietitian will administer a phone interview to determine what participants have eaten on the randomly selected days (described above in Section 3.2.3).

An online, confidential, Diet History Questionnaire (DHQ) will be used to assure adherence with the study diet and will be completed at baseline and week 12. Patients will complete the online questionnaire at home immediately prior to or immediately following their baseline and week 12 visit. Alternatively, they may be able to complete it in the clinic if a computer with internet access is available. We will use the National Cancer Institute's web-based DHQ II questionnaire that asks about food eaten in the past 30 days. There is no patient identifying information in the DHQ. Patients log into the questionnaire with a unique code and password. The DCC will download an Excel file containing study participants' questionnaire responses from a secure https website accessible only by certain study staff at the DCC.

Study diet satisfaction surveys will be administered via an online questionnaire at the time points described in section 3.2.3. This will be a brief survey that will allow for free text comments from participants about their satisfaction and overall experience with the assigned diet.

The Patient Reported Outcome Measurement System (PROMIS) questionnaire contains several measures previously shown to correlate with disease activity and to have construct validity in CD. These include measures of fatigue, pain interference, social aspects, and sleep.

A subset of core variables found in the Multi-dimensional Health Assessment Questionnaire (MD-HAQ) will be used to assess physical function and joint pain.

We will screen for inflammatory back pain using criteria developed by Sieper et al. and assess symptom severity with the Bath AS Functional index in those who screen positive.

We will assess quality of life using a Short Quality of Life in Inflammatory Bowel Disease Questionnaire (SIBDQ) at all visits.

Patient's most recent colonoscopy results prior to the time of randomization will also be collected for those subjects with accessible records. Additionally, any colonoscopies conducted during the study or within 6 weeks of the termination visit may be requested at the opinion of the Principle Investigator.

### **7.12 Efficacy Evaluations**

Crohn's Disease Activity Index(CDAI), PRO2 and PRO3 measures, and Short Crohn's Disease Activity Index (sCDAI) will be used to determine if participants' symptoms have improved or worsened with the intervention. The sCDAI assesses clinical remission as defined by patient reported outcomes focusing on the cardinal symptoms of CD - diarrhea, abdominal pain, and general wellbeing. The CDAI uses patient reported measures, similar to the sCDAI, but also uses findings from a physical exam and laboratory measures.

## **8 Statistical Plan**

### **8.1 Primary Endpoint**

The primary outcome will be measured at 6 weeks after the start of the study diets. Specific aim 1 will focus on the outcomes that are most important to patients, specifically the control of the cardinal symptoms of CD. We will assess clinical remission as defined by patient reported outcomes (PROs) focusing on the cardinal symptoms of CD - diarrhea, abdominal pain, and general wellbeing. These have

been combined into the Short Crohn's Disease Activity Index (sCDAI) which provides a composite measure of the PROs. Symptomatic remission will be defined as a sCDAI <150^74 in the absence of the need for increasing corticosteroid dose or initiation of new therapies for CD during the study period. Participants who withdraw from the study prior to week 6 will be categorized as failing to achieve symptomatic remission and other related outcomes.

The sCDAI was derived from the Crohn's Disease Activity Index, the standard disease activity index for CD clinical trials in adults for the last several decades. The original index includes the number of liquid stools per day, abdominal pain, general wellbeing, extraintestinal complications of CD, use of Lomotil or opiates for diarrhea, anemia, weight loss, and the presence of an abdominal mass on physical exam. The CDAI has increasingly fallen out of favor as it combines PROs with physical exam, medication use, and laboratory data. As such, investigators validated the sCDAI which patients can complete using a simple web-based survey tool without an office visit or blood draw. The sCDAI uses the same scale as the full CDAI, such that scores <150 define remission, 150-219 mild activity, 220-450 moderate activity, >450 severe activity. The correlation between the full CDAI and sCDAI for baseline scores and score change was 0.90 and 0.96, respectively. Our research team has subsequently demonstrated that the sCDAI can be accurately measured with less than 7 days of data, thereby reducing participant burden (IR-1). Indeed, we have utilized this abbreviated version of the sCDAI as part of the CCFA Partners PPRN since its inception and in our ongoing RCT of a high vs. low red meat diet for patients with quiescent CD that is being conducted within the CCFA Partners PPRN.

The primary outcome will be measured at 6 weeks. The 6 week study duration was selected for the following reasons:

- a. Our stakeholders informed us that they would be unlikely to continue trying a dietary therapy if they did not observe a benefit within 6 weeks.
- b. In Breaking the Vicious Cycle, it is stated that one month is sufficient to know if the SCD is working.
- c. The practical implications of not allowing changes to the medical therapy for patients with active CD for much longer than 6 weeks could be a major disincentive to enrollment.

